4.7.3 Electrocardiogram (ECG) Evaluations

A summary of abnormal clinically significant and abnormal not clinically significant electrocardiogram (ECG) results will be presented by treatment and visit. Absolute and change from baseline ECG results will be tabulated (Heart Rate, PR interval, QRS interval, RR interval, QT interval, QTcF interval) by treatment group and overall. QT and QTc will be analyzed in accordance with ICH E14 guidance. All ECG tests and results will be listed. A summary of Electrocardiogram Abnormal Results (QT and QTcF) will be presented by treatment and visit. Also a shift table for QT and QTcF for interval class will be presented for the baseline measurement versus the endpoint measurement by treatment and visit.

If multiple ECG evaluations were performed at baseline, the latest non-missing measurement prior to the first administration of study treatment will be used for the baseline value. For multiple ECG evaluations at post-baseline visits occurring during the same visit window, the closest measurement to the actual visit date will be used for the analyses and summary tables. When two measurements are exactly equidistant to the exact visit date, the later will be used for the analyses and summary tables.

All ECG tests and results will be listed.

4.7.4 Vital Signs Evaluations

The raw scores and change from baseline results of blood pressure, heart rate, temperature, body weight and BMI will be summarised by treatment and visit.

For each vital signs variable, the Baseline value is defined as the last non-missing measurement collected/derived prior to the first study medication administration at Baseline visit.

Vital signs will be presented for individual subjects in data listings.

If multiple Vital signs evaluations were performed at baseline, the latest non-missing measurement prior to the first administration of study treatment will be used for the baseline value. For multiple Vital signs evaluations at post-baseline visits occurring during the same visit window, the closest measurement to the actual visit date will be used for the analyses and summary tables. When two measurements are exactly equidistant to the exact visit date, the later will be used for the analyses and summary tables.

4.7.5 Other measures

4.7.5.1 Concomitant Medications and procedures and medication history

Medication history refers to the medications that the study subjects stopped taking before or at baseline. Concomitant medications are defined as medications taken from baseline through the end of the study. Counts and percentages of subject used for each medication will be computed and

summarised by ATC level 2, level 4 and preferred term for each treatment and overall. If coding levels are empty, text "Uncoded" will be displayed.

All procedures will be listed.

4.8 Physical Examinations

Data has been documented into AE or medical history. No separate analysis will be performed.

Appendix 1: Major or Minor PDs

Vifor DVSCAT (Categories of PDs)	Vifor DVDECOD (Sub-Categories of PDs)	Details	Major or Minor
ICF PROCEDURE ERROR	ICF PROCEDURE ERROR	Written informed consent obtained after study specific procedure conducted	Major
	PRE-ICF PROCEDURE	Written informed consent not obtained and study specific procedure conducted	Major
INCLUSION CRITERIA	INCLUSION CRITERION # 1	At least 18 years of age Deviation: <18 years	Major
	INCLUSION CRITERION # 2	Hb <11 g/dL (females) or Hb <12 g/dL (males) at the screening visit Deviation: Hb >=11 g/dL (females) or Hb >=12 g/dL (males) at screening visit	Major
	INCLUSION CRITERION # 3	Serum ferritin <100 ng/mL for subjects with underlying inflammatory disease (e.g., inflammatory bowel disease (IBD), chronic kidney disease (CKD) or chronic heart failure (CHF), as determined by C-reactive protein [CRP] levels above the normal range) otherwise ≤14 ng/mL in subjects with no apparent underlying inflammatory disease (as determined by CRP levels within normal range) at the screening visit Deviation: Serum ferritin >=100 ng/mL for subjects with underlying inflammatory disease (CRP level above NR) at screening visit Serum ferritin >14 ng/mL for subjects without underlying inflammatory disease (CRP level within NR) at screening visit	Major
	INCLUSION CRITERION # 4	TSAT <16% (any subject) at the screening visit Deviation: TSAT >=16 % at screening visit	Major
	INCLUSION CRITERION # 5	Microcytic, hypochromic anaemia defined as: a. Mean corpuscular Hb concentration (MCHC) <32% b. Mean corpuscular volume (MCV) < 80 fL c. Mean corpuscular Hb (MCH) <27 pg Deviation: MCHC >=32% or MCV >= 80fL or MCH >=27 pg at screening	Major
	INCLUSION CRITERION # 6	Any history of iron deficiency (e.g. iron deficiency anaemia) at screening visit	Major
EXCLUSION CRITERIA	EXCLUSION CRITERION # 1	Subject has known hypersensitivity to any of the products to be administered during dosing	Major
	EXCLUSION CRITERION # 2	Any history of iron storage diseases such as haemochromatosis	Major
	EXCLUSION CRITERION # 3	Any history or clinical findings of iron utilisation disorders such as sideroachrestic anaemia	Major
	EXCLUSION CRITERION # 4	Known haemoglobinopathy (e.g. thalassaemia)	Major
	EXCLUSION CRITERION # 5	Any history or clinical findings of an anaemia associated with: a. Haematuria b. Vitamin B12 or folic acid deficiency that requires treatment (subjects can be included after deficiency	Major

Vifor DVSCAT (Categories of PDs)	Vifor DVDECOD (Sub-Categories of PDs)	Details	Major or Minor
		is corrected)	
	EXCLUSION CRITERION # 6	Any allergic predisposition, ie any history of asthma or atopic allergy. This includes drug allergies.	Major
	EXCLUSION CRITERION # 7	Planned surgery with anticipated blood loss (defined as Hb drop >2 g/dL) in the 3 months post randomisation	Major
	EXCLUSION CRITERION # 8	Subject has known malignancy (with or without current treatment), except basal cell or squamous cell carcinoma of the skin or cervical intra-epithelial neoplasia	Major
	EXCLUSION CRITERION # 9	Haemodialysis (current or planned within the next 3 months)	Major
	EXCLUSION CRITERION # 10	History of IV iron therapy, erythropoiesis stimulating agent (ESA) therapy and/or blood transfusion in previous 4 weeks prior to screening, and oral iron or oral iron-containing products including Chinese herbal medicines (>75mg iron/day) in the 7 days prior to screening	Major
	EXCLUSION CRITERION # 11	Body weight <35 kg	Major
	EXCLUSION CRITERION # 12	Chronic liver disease and/or screening alanine transaminase (ALT) or aspartate transaminase (AST) above 3 times the upper limit of the normal range	Major
	EXCLUSION CRITERION # 13	Known human immunodeficiency virus infection, acquired immunodeficiency syndrome, tuberculosis	Major
	EXCLUSION CRITERION # 14	Known active hepatitis B or C or other active infection (acute or chronic)	Major
	EXCLUSION CRITERION # 15	Subject currently is enrolled in or has not yet completed at least 30 days since ending other investigational device or drug study(ies), or subject is receiving other investigational agent(s)	Major
	EXCLUSION CRITERION # 16	Subject is pregnant or is breast feeding	Major
	EXCLUSION CRITERION # 17	Female subject of childbearing potential not using adequate contraceptive methods during the study and for up to 1 month after the last dose of the study medication. Adequate contraceptive methods are defined as those which result in a low failure rate (I.e., less than 1% per year) when used consistently and correctly such as implants, injectables, combined oral contraceptives, some intra-uterine devices, sexual abstinence or vasectomised partner. Non-childbearing potential includes being surgically sterilised at least 6 months prior to the study or post-menopausal, defined as amenorrhoea for at least 12 months.	Major
	EXCLUSION CRITERION # 18	Male subjects fathering a child within 7 days from the last study drug administration	Major
	EXCLUSION CRITERION # 19	Subject has any kind of disorder that compromises the ability of the subject to give written informed consent and/or to comply with study procedures and/or other reason(s) that render subject not appropriate for study participation in the opinion of the treating physician	TBD*
NON- COMPLIANCE WITH STUDY	NON-COMPLIANCE WITH STUDY DRUG # 1	Incomplete FCM dose administered on Day 1, Day 8 or Day 15	TBD*

Vifor DVSCAT (Categories of PDs)	Vifor DVDECOD (Sub-Categories of PDs)	Details	Major or Minor
DRUG			
	NON-COMPLIANCE WITH STUDY DRUG # 2	Incomplete IS dose administered	TBD*
STUDY DRUG ADMINISTRATION/TECHNICAL ERROR	STUDY DRUG ADMINISTRATION/TECHNICAL ERROR # 1	FCM Dose not administered according to visit schedule (as per table 2 in protocol)	TBD*
	STUDY DRUG ADMINISTRATION/TECHNICAL ERROR # 2	Total daily FCM Dose not administered according to body weight and Hb	TBD*
	STUDY DRUG ADMINISTRATION/TECHNICAL ERROR # 3	Incorrect FCM administration times (infusion of 500 mg < 5 min OR infusion of 1000mg < 15 min AND for both doses >30 min) Major for rapid administration (< 5min for 500 mg dose or <15 min for 1000mg dose); Minor for longer administration (>30 min)	Major/Minor
	STUDY DRUG ADMINISTRATION/TECHNICAL ERROR # 4	FCM diluted with the incorrect volume (infusion of 500 mg NOT diluted in 100mL OR infusion of 1000mg NOT diluted in 250mL) For over dilution in larger volume: Major For dilution in smaller volume(<100ml for 500mg dose or <250ml for 1000mg dose: Minor	Major/Minor
	STUDY DRUG ADMINISTRATION/TECHNICAL ERROR # 5	IS Dose not administered according to Ganzoni formula	TBD*
	STUDY DRUG ADMINISTRATION/TECHNICAL ERROR # 6	IS Dose not administered according to visit schedule Major for overdose (> 3 doses per week) Minor for dose omission	Major/Minor
	STUDY DRUG ADMINISTRATION/TECHNICAL ERROR # 7	Maximum daily IS dose exceeded(> 200mg)	Major
	STUDY DRUG ADMINISTRATION/TECHNICAL ERROR # 8	IS diluted with the incorrect volume (Dilution of 10 ml of the product intended for slow IV push injection OR drip infusion of 10 ml diluted in > 200ml)	Major
	STUDY DRUG ADMINISTRATION/TECHNICAL ERROR # 9	Incorrect IS administration time (infusion >60 mins)	Minor
	STUDY DRUG ADMINISTRATION/TECHNICAL ERROR # 10	Incorrect IS administration time (for undiluted injection< 10 mins OR for diluted drip infusion < 30 mins)	Major
STUDY DRUG DEVIATION	STUDY DRUG DEVIATION # 1	Incorrect IMPs storage condition (FCM store > 30°C or freeze / IS store < 4°C or > 25°C or freeze)	TBD*
	STUDY DRUG DEVIATION # 2	Incorrect treatment administration vs randomization	Major
	STUDY DRUG DEVIATION # 3	Study drug not stopped when subject experienced any kind of hypersensitivity reaction related to the study drug during administration	Major

Vifor DVSCAT (Categories of PDs)	Vifor DVDECOD (Sub-Categories of PDs)	Details	Major or Minor
PROHIBITED MEDICATION	PROHIBITED MEDICATION	Prohibited Therapy and Concomitant Treatment (Oral or other IV iron therapy (other than the study medication), multivitamins or nutritional supplements containing iron > 75 mg per day, ESAs, Blood transfusions)	Major
PROCEDURE/TEST NOT DONE	PROCEDURE/TEST NOT DONE # 1	Vital Signs missing	Major
	PROCEDURE/TEST NOT DONE # 2	Physical Examination missing (Fully missing is Major at Screening/Fully missing is Minor at EOS/Partially missing is Minor at Screening and EOS)	Major/Minor
	PROCEDURE/TEST NOT DONE # 3	Laboratory tests: Haematology & Iron status missing from Visit 2 to Visit 6(Missing assessment is major/Missing parameter is minor)	Major/Minor
	PROCEDURE/TEST NOT DONE # 4	Laboratory tests: Haematology & Iron status missing at Visit 1(Missing assessment is major/Parameters Hb, MCH, MCV, MCHC, Serum Ferritin, TSAT missing is major/Other parameters missing is minor)	Major/Minor
	PROCEDURE/TEST NOT DONE # 5	Laboratory tests : Chemistry missing from Visit 2 to Visit 6 (Missing assessment is major/Missing parameter is minor)	Major/Minor
	PROCEDURE/TEST NOT DONE # 6	Laboratory tests: Chemistry missing at Visit 1(Missing assessment is major/Parameters CRP, ALT, AST missing is major /Other parameters missing is minor)	Major/Minor
	PROCEDURE/TEST NOT DONE # 7	Laboratory tests at planned visits: Urinalysis missing (Missing assessment is major/Missing parameter is minor)	Major/Minor
	PROCEDURE/TEST NOT DONE # 8	Laboratory tests: Hepatitis B and C missing at Visit 1 (Any parameters missing is major)	Major
	PROCEDURE/TEST NOT DONE # 9	ECG missing	Minor
	PROCEDURE/TEST NOT DONE # 10	Laboratory tests: Pregnancy Test at Screening missing	Major
	PROCEDURE/TEST NOT DONE # 11	Laboratory tests: Pregnancy Test at Visit 6 missing	Major
PROCEDURE OUTSIDE WINDOW	PROCEDURE OUTSIDE WINDOW # 1	Laboratory tests Out Of planned Window	Minor
	PROCEDURE OUTSIDE WINDOW # 2	Vital Signs out of planned window	Minor
	PROCEDURE OUTSIDE WINDOW # 3	ECG Out Of planned Window (Not done at Screening & Week 4 & EOS)	Minor
NON- COMPLIANCE WITH PROCEDURE	NON-COMPLIANCE WITH PROCEDURE #1	Dosing NOT performed after all study assessments for the visit(Out of chronological order is minor)	Minor
	NON-COMPLIANCE WITH PROCEDURE #2	Missing reporting of SAEs to sponsor within the agreed timeframe "within 24 hours of awareness"	Major
VISIT OUTSIDE WINDOW	VISIT OUTSIDE WINDOW # 1	Screening duration > 7 days	Minor
	VISIT OUTSIDE WINDOW # 2	visits out of window (Planned chronological visits schedule not respected is major)	Major
VIST NOT DONE	VISIT NOT DONE	Visits NOT done	Major

Vifor DVSCAT (Categories of PDs)	Vifor DVDECOD (Sub-Categories of PDs)	Details	Major or Minor
SUBJECT NOT WITHDRAWN AS PER PROTOCOL	SUBJECT NOT WITHDRAWN AS PER PROTOCOL	Site staff failed to take the appropriate action in response to protocol-specific discontinuation/withdraw criteria such as: severe anaemia (Hb <6 g/dL) and the subject continued the study	Major
OTHER	NON-COMPLIANCE WITH PROCEDURE # 1	Rescreening within 4 weeks of original screening visit(minor)	Minor
	NON-COMPLIANCE WITH PROCEDURE # 2	Race is not Chinese and subject randomized (minor)	Minor
	OTHER	Any other protocol deviation (e.g., as outlined in the monitoring plan):	TBD*
NOTE		*TBD (to be discussed): PDs will be determined of major or minor by TMM and consult with Sponsor if necessary CRA will submit the signed and dated major protocol deviation to local EC within 15 working days.	

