5.2 Inclusion Criteria

Investigators will be expected to maintain a screening log of all potential study candidates that includes minimum key information about the potential candidate, date, and outcome of the screening process (e.g., enrolled into study, reason for ineligibility, or refused to participate). The following inclusion criteria must be met for each subject:

1. At least 18 years of age.
2. Hb < 11 g/dL (females) or <12 g/dL (males) at screening visit
3. Serum ferritin <100 ng/mL for subjects with underlying inflammatory disease (e.g. IBD, CKD or CHF, as determined by high sensitive C-reactive protein (hsCRP) levels above the normal range) otherwise serum ferritin \leq 14 ng/mL in subjects with no apparent underlying inflammatory disease (as determined by hsCRP levels within normal range) at the screening visit
4. TSAT <16% (any subject) at the screening visit.
5. Microcytic, hypochromic anaemia at the screening visit, defined as:
 - a. MCHC < 32%
 - b. MCV < 80 fL
 - c. MCH < 27 pg
6. Subjects with the ability to understand the requirements of the study and abide by the study restrictions, and who agree to return for the required assessments
7. Before any study-specific procedure is conducted, the appropriate written informed consent must be obtained.

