5.3 Exclusion Criteria

1. Subject has known hypersensitivity to any of the products to be administered during dosing.
2. Any history of iron storage diseases such as haemochromatosis.

3. Any history or clinical findings of iron utilisation disorders such as sideroachrestic anaemia
4. Known haemoglobinopathies (e.g. thalassaemia).
5. Any history or clinical findings of anaemia associated with:
 - a. Haematuria
 - b. Vitamin B12 or folic acid deficiency that requires treatment (subjects can be included after deficiency is corrected)
6. Any allergic predispositions, i.e. any history of asthma or atopic allergy. This includes drug allergies.
7. Planned surgery with anticipated blood loss (defined as Hb drop >2 g/dL) in the 3 months post-randomisation.
8. Subject has known malignancy (with or without current treatment), except basal cell or squamous cell carcinoma of the skin or cervical intra-epithelial neoplasia.
9. Haemodialysis (current or planned within the next 3 months).
10. History of IV iron therapy, erythropoiesis stimulating agent (ESA therapy and/or blood transfusion in previous 4 weeks prior to baseline, and oral iron or iron-containing products including Chinese herbal medicines (>75 mg iron/day) in the 7 days prior to baseline.
11. Body weight <35 kg.
12. Chronic liver disease and/or screening ALT or AST above 3 times the upper limit of the normal range.
13. Known human immunodeficiency virus infection, acquired immunodeficiency syndrome, tuberculosis.
14. Known active hepatitis B or C or other active infection (acute or chronic).
15. Subject currently is enrolled in or has not yet completed at least 30 days since ending other investigational device or drug study(ies), or subject is receiving other investigational agent(s).
16. Subject is pregnant or is breast feeding.

17. Female subject of childbearing potential is not using adequate contraceptive methods during the study and for up to 1 month after the last dose of the study medication. Adequate contraceptive methods are defined as those which result in a low failure rate (i.e., less than 1% per year) when used consistently and correctly such as implants, injectables, combined oral contraceptives, some intra-uterine devices, sexual abstinence or vasectomised partner. Non-childbearing potential includes being surgically sterilised at least 6 months prior to the study or post-menopausal, defined as amenorrhoea for at least 12 months.

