3.3 Per Protocol Set

The Per-Protocol Set (PPS) is defined as all subjects in the FAS with a study drug compliance between 80 and 120% and do not have any major protocol violations ([appendix 1](#)).

The subjects in the PPS will be analysed based on the treatment that they were randomised to.

As per protocol, blood samples had to be drawn before study drug administration (when planned). All laboratory efficacy assessments (Hb, Ferritin, and TSAT) that are measured from a blood sample

taken after the study drug administration will not be considered for any efficacy analysis for both PPS and FAS. The subjects will still be in the PPS if they do not have a major protocol deviation.

For subjects who took prohibited concomitant medication, all laboratory efficacy assessments (Hb, Ferritin, and TSAT) will be censored after the prohibited medication start date for both PPS and FAS. The subjects will still be in the PPS if they do not have a major protocol deviation.

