4.1.6 Analysis Sets

The analysis of the primary endpoint will be performed for the Per Protocol set (PPS) and tested at a one sided alpha level of 2.5% with a 15% non-inferiority margin. A sensitivity analysis will be performed on the Full Analysis Set (FAS). All secondary endpoints will be analysed on the FAS and the PPS. All statistical tests will be performed at a 5% level (2-sided).

All safety analyses will be performed on the Safety Set.

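### SAP Appendix 1, which decides PPS membership for the primary test, departs from the protocol on two eligibility rows and leaves the prohibited-medication rule of SAP 3.3 without effect in the PPS

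*SAP*

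**What the plan says.** Protocol 11.3.2 leaves the definition of major violations to the SAP. SAP 3.3 builds the PPS from FAS subjects with 80–120% compliance and no major violation listed in Appendix 1. Under SAP 4.1.6 the primary endpoint is analysed on the PPS, "tested at a one sided alpha level of 2.5% with a 15% non-inferiority margin", and the FAS is a sensitivity analysis. SAP 4.6.1 applies the test to both sets.

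- **Exclusion #10.** Protocol 5.3 refers to "blood transfusion in previous 4 weeks prior to baseline, and oral iron or iron-containing products including Chinese herbal medicines", with the oral-iron window also ending at baseline. The synopsis uses the same anchor. The Major row in Appendix 1 instead reads "blood transfusion in previous 4 weeks prior to screening, and oral iron or oral iron-containing products", and both of its windows end at screening.
- **Inclusion #6.** Protocol 5.2 asks for "Subjects with the ability to understand the requirements of the study and abide by the study restrictions". The Major row with that number in Appendix 1 reads "Any history of iron deficiency (e.g. iron deficiency anaemia) at screening visit".
- **Prohibited medication.** SAP 3.3 censors Hb, ferritin and TSAT after the start of prohibited medication in both PPS and FAS, then adds: "The subjects will still be in the PPS if they do not have a major protocol deviation". The Appendix 1 row begins "Prohibited Therapy and Concomitant Treatment (Oral or other IV iron therapy (other than the study medication", goes on to name higher-dose iron supplements, ESAs and transfusions, and is rated Major without qualification.
- **Rescue and missing data.** Protocol 7.7 names transfusion and ESAs as possible rescue, with withdrawal and end-of-study procedures first. SAP 4.1.8 imputes no missing efficacy data.
- **Windows.** Appendix 1 rates laboratory tests outside the window Minor. The visit row reads "visits out of window (Planned chronological visits schedule not respected is major" and is rated Major.

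**The concern.** Because the primary non-inferiority test is run on the PPS, an error in Appendix 1 is an error in the primary analysis set. A wrong anchor date on prior iron, ESA or transfusion matters because those treatments can move Hb, which is the endpoint. It can remove subjects who met the protocol and overlook subjects who did not.

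Rescue raises a different issue. A subject who needs a transfusion or ESA for symptomatic anaemia will often be a treatment failure. If that subject is dropped and not counted as a non-responder, the response rate in that arm rises. In an open-label trial, such questions are better settled in writing than case by case.

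**Working it through.** **1. The plan's own figure.** The inputs are 70% response on IS, a 15-point margin, one-sided 2.5%, 80% power and 20% drop-out (Protocol 11.2, SAP 2.4). No FCM rate is stated, so I take it as equal to IS.

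n per arm = (1.960 + 0.842)² × (0.70×0.30 + 0.70×0.30) / 0.15² = 7.85 × 0.42 / 0.0225 ≈ 146.5, so 147. Then 147 / 0.80 = 183.75, so 184 per arm and 368 in total. The stated sizes reproduce.

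**2. Exclusion #10.** Screening runs from Day -7 to Day -1, and dosing is on Day 1. Take a subject screened on Day -7.

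| Event | Protocol 5.3 (to baseline) | Appendix 1 (to screening) |
|---|---|---|
| Last oral iron the day before screening | 8 days before baseline: accepted | 1 day before screening: Major |
| IV iron 30 days before baseline | outside 4 weeks: accepted | 23 days before screening: Major |
| ESA or transfusion on Day -3 | inside 4 weeks: violation | after screening: not caught by this row |

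The mismatch runs in both directions, and its width is at most the 7-day screening period.

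**3. Inclusion #6.** Inclusion rows #1 to #5 each spell out what counts as a deviation; row #6 does not. Read as a requirement, it is met by anyone with iron deficiency anaemia at screening, which Inclusion #2 to #5 already establish. Read as the deviation itself, it flags every eligible subject and empties the PPS. The protocol's actual criterion is absent under either reading.

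**4. Prohibited medication.** Under SAP 3.3 retention depends on having no major deviation. Under Appendix 1 the prohibited medication is itself a major deviation, so no user can meet the condition. The PPS half of the 3.3 rule is empty; its censoring still operates in the FAS.

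**5. What removal of rescued failures could do.** The documents give no rescue rates, so those below are assumptions. Set the truth at the margin with every failure counted: IS 70%, FCM 55%, 147 per arm. Suppose all rescued subjects are non-responders and are removed. With rescue fraction r, the PPS rate is p / (1 − r) on about 147 × (1 − r) subjects.

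For 5% on FCM and 0% on IS, the FCM rate is 0.55 / 0.95 = 0.579 on 140 subjects and IS is 0.70 on 147. SE = √(0.579×0.421/140 + 0.70×0.30/147) = 0.0563. P(non-inferiority) = Φ((0.579 − 0.700 + 0.15)/0.0563 − 1.960) = Φ(−1.446) = 7.4%.

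The last column enumerates the continuity-corrected Newcombe interval of SAP 4.6.1 exactly.

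| Rescue FCM / IS | PPS rates FCM / IS | False NI, Wald | False NI, Newcombe |
|---|---|---|---|
| none removed | 55.0% / 70.0% | 2.5% | 2.2% |
| 2% / 0% | 56.1% / 70.0% | 3.9% | 3.5% |
| 5% / 2% | 57.9% / 71.4% | 4.5% | 3.9% |
| 5% / 0% | 57.9% / 70.0% | 7.4% | 6.6% |
| 10% / 5% | 61.1% / 73.7% | 6.3% | 5.6% |
| 2% / 2% | 56.1% / 71.4% | 2.2% | 2.0% |
| 5% / 5% | 57.9% / 73.7% | 1.8% | 1.5% |
| 0% / 5% | 55.0% / 73.7% | 0.4% | 0.3% |

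The direction depends entirely on which arm has more rescue.

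**The case against.** The case on the other side has force on several points.

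- **Newly diagnosed subjects.** A reader might infer that Inclusion #6 costs the trial subjects diagnosed for the first time at screening. The documents do not support this. Protocol 10.2.4 treats a condition present at screening, with IDA as its example, as pre-existing and sends it to the medical history page, so such a subject meets the row.
- **Treatment between screening and baseline.** Other provisions may pick it up. The prohibited-medication row has no start-date limit, Appendix 1 has a catch-all row, and Protocol 15.1 allows case-by-case rating. That softens the missed cases. It does not help the subject rated Major for a washout the protocol accepts.
- **SAP 3.3 against Appendix 1.** A reader might call this a flat contradiction. It is not, because the 3.3 sentence is conditional and so defers to Appendix 1. What stands is that the condition can never be met. If 3.3 meant no other major deviation, the passages would conflict directly.
- **Rescue.** Leaving prohibited-medication users out of a per-protocol set is conventional. Rescue after protocol-compliant withdrawal might not be logged as a deviation, and the documents do not settle this. Rescued subjects who qualify stay in the FAS, where the test is also run.
- **Visit windows.** A reader might see a contradiction with the Minor rating for laboratory tests. The parenthesis can be read as confining Major to visits out of sequence, so this is an ambiguity only.

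**Conclusion.** Two Major rows that govern the primary analysis set do not match the protocol, and one rule in SAP 3.3 has no effect in the PPS. Exclusion #10 is the firmest of these, because it changes who enters the PPS on a plain reading. Inclusion #6 is the wrong criterion, though it probably excludes nobody. On prohibited medication, the literal text drops a rescued non-responder from the primary denominator, and no statement says how a censored subject counts in the FAS.

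The size of any bias is an assumption. False non-inferiority is about 4–7% when rescue is 2–5 points more frequent on FCM, and below 2.5% when rescue is equal or more frequent on IS. It would be tempting to conclude that the plan favours FCM, but no rescue rates are given and nothing in the documents supports that direction. I take the protocol supplied to be the version 5.0 that the SAP names. The planned 147, 184 and 368 stand.

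**What to change.** Before database lock:

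1. Replace the Inclusion #6 and Exclusion #10 rows of Appendix 1 with the protocol's text, so that both Exclusion #10 windows end at baseline.
2. Reconcile SAP 3.3 with the prohibited-medication row. Either say that such use removes the subject from the PPS and delete the retention sentence for these subjects, or say that it does not by itself remove the subject and re-rate the row. State whether rescue given after withdrawal counts as a deviation.
3. State that a subject censored for prohibited medication counts as a non-responder unless response was already reached before its start. Apply this at least in the FAS test and in a PPS sensitivity analysis that keeps these subjects.
4. Clarify whether Major in the visit-window row applies only to visits out of order.

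The cost is a few SAP edits and one extra sensitivity table. No new data and no change in sample size are needed. Counting rescued subjects as failures may lower the response rate slightly in either arm.

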11.7 Efficacy Evaluations

11.7.1 Primary

The primary endpoint is the percentage of subjects achieving an increase in Hb of ≥ 2 g/dL (responders) from baseline at any time up to Week 8. The non-inferiority test will be applied to the difference between the proportions of subjects meeting the primary endpoint using the PPS. Non-inferiority will be determined if the lower bound of the 95% CI of this difference is above the non-inferiority margin as defined in Section 11.2. Further details will be specified in the SAP.

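### Primary per-protocol set drops subjects for procedural lapses unrelated to haemoglobin, and leaves key dosing exclusions to open-label judgement

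*SAP*

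**What the plan says.** Protocol 11.7.1 places the confirmatory test on the PPS: "The non-inferiority test will be applied to the difference between the proportions of subjects meeting the primary endpoint using the PPS". SAP 4.1.6 repeats this and adds "A sensitivity analysis will be performed on the Full Analysis Set (FAS"). SAP 4.6.1 applies the same –15% criterion to both sets.

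Protocol 11.3.2 leaves major violations to the SAP. SAP 3.3 defines the PPS as "all subjects in the FAS with a study drug compliance between 80 and 120% and do not have any major protocol violations", pointing directly to Appendix 1. That appendix rates as Major, among others:

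- any missing vital signs;
- a chemistry panel wholly missed at Visits 2 to 6;
- "Laboratory tests at planned visits: Urinalysis missing (Missing assessment is major/Missing parameter is minor");
- "Laboratory tests: Pregnancy Test at Visit 6 missing";
- "Missing reporting of SAEs to sponsor within the agreed timeframe" (24 hours).

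Dosing items with a fixed Major rating number four for IS: more than three doses a week, more than 200 mg in a day, wrong dilution, and "Incorrect IS administration time (for undiluted injection< 10 mins OR for diluted drip infusion < 30 mins"). There are two for FCM: too-rapid administration and over-dilution. An incomplete dose in either arm, and a dose not given according to Table 2 or the Ganzoni formula, are marked TBD. The note to the appendix says "PDs will be determined of major or minor by TMM and consult with Sponsor if necessary".

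**The concern.** One label does two jobs. Major marks deviations serious enough to report (the appendix note sends them to the ethics committee), and it also decides who enters the primary analysis. A missed urine sample or a late SAE report is a conduct matter. It says nothing about whether Hb rose by 2 g/dL or whether the iron was given as planned. Removing such subjects shrinks the primary set and departs from the randomised comparison with no gain in assay sensitivity.

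The dosing items raise a different problem. They arise at each administration, and IS is given more often, so equal care per administration still excludes more IS subjects. The TBD items leave PPS membership to be decided after the event in an open-label trial. The SAP does not say when this happens or whether the decision is made without sight of arm and response.

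**Working it through.** **Reproducing the plan's sample size.** Inputs from Protocol 11.2 and SAP 2.4: 70% response in IS (taken as equal in FCM), margin 15 points, one-sided 2.5%, 80% power, 20% drop-out.

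- n = 2 × 0.70 × 0.30 × (1.960 + 0.842)² / 0.15² = 146.5, so 147 per arm.
- 147 / 0.80 = 183.75, so 184 per arm and 368 in total. Both figures agree with the plan.
- By the same normal approximation, power at 147 per arm is 80.1%. Exact binomial enumeration of the interval named in SAP 4.6.1 (Newcombe's Wilson score with continuity correction) gives 78.7%. The rows below use the exact method.

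**Procedural triggers.** From Visit 2 onward the schedule of events gives 5 vital-sign, 5 chemistry and 4 urinalysis assessments, plus 1 pregnancy test for women of childbearing potential: at most 15. Let q be the miss rate. It is an assumption. The share excluded is 1 – (1 – q)^k, with k = 15 if misses are independent and k = 5 if they cluster by visit. Exclusions are taken as additional to the 20%.

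| q | k | Excluded | PPS per arm (from 147) | Exact power |
|---|---|---|---|---|
| 0.5% | 5 | 2.5% | 143 | 77.2% |
| 1% | 5 | 4.9% | 140 | 76.6% |
| 0.5% | 15 | 7.2% | 136 | 75.2% |
| 1% | 15 | 14.0% | 126 | 71.9% |

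**Dosing triggers.** Protocol 2.1 takes a 65 kg subject with Hb 9 g/dL: 65 × (15 – 9) × 2.4 + 500 = 1,436 mg, which is 7 IS doses against 2 FCM doses. The maximum is 11 for IS (Protocol 7.2.2), against 1 to 3 for FCM (Table 2 and its footnote). With an assumed equal error rate e per administration, the share with at least one error is:

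- e = 1%: FCM 1 – 0.99² = 2.0%; IS 1 – 0.99⁷ = 6.8%.
- e = 2%: FCM 1 – 0.98² = 4.0%; IS 1 – 0.98⁷ = 13.2%.

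**Possible shift in the difference.** Suppose 70% truly respond in each arm and a proportion r of the excluded subjects respond. An arm that loses a fraction x then shows (0.70 – x·r) / (1 – x). For r from 40% to 90%, the FCM – IS difference moves by –1.6 to +1.1 points at e = 1%, and by –3.3 to +2.2 points at e = 2%. At e = 1% and r = 40%, for example, FCM shows (0.70 – 0.020 × 0.40) / 0.980 = 70.6% and IS (0.70 – 0.068 × 0.40) / 0.932 = 72.2%. The sign depends on whether excluded subjects respond worse or better than the rest.

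**The case against.** **Size.** The miss rates are not in the documents, and independence is doubtful because vital signs, blood and urine are taken at the same visits. A wholly missed visit is Major in its own right and loses the Hb sample too. The pregnancy test applies only to some women. Since 147 is the number for a test run on the PPS, the 20% may be read as covering the whole gap from randomised to evaluable. All of this stands: on the clustered assumption the cost is about two points of power, and there may be none.

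**Arm imbalance.** A reader might infer that the urinalysis, vital-sign and pregnancy-test rules penalise IS. They do not. The assessment schedule is common to both arms, and Protocol 9.2.2 adds no procedures at the extra IS dosing visits beyond adverse-event and medication updates. The imbalance comes only from dosing items, and an omitted IS dose or an over-long IS infusion is Minor. Timing and dilution also concern treatment delivery (Protocol 7.2.1 restricts FCM dilution for stability reasons), so excluding those subjects from a per-protocol set is defensible.

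**Unmasked selection.** A reader might also infer that staff will classify TBD items knowing arm and Hb. The SAP does not define TMM or say what TMM sees. The gap is the missing statement on timing and masking, in an open-label trial where knowledge of arm is likely. It is not proof of selective exclusion.

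**Role of the full analysis set (FAS).** SAP 4.6.1 tests both sets and each has its own table, which mitigates the problem. The PPS is still named as primary, with the FAS as sensitivity, and the plan does not say how a disagreement would be interpreted.

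Protocol 15.1 speaks of case-by-case assessment, but it sends the criteria to the SAP, and the SAP fixes the procedural items as Major.

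**Conclusion.** The definition is too broad. Followed as written, SAP 3.3 and Appendix 1 remove subjects with usable Hb data from the confirmatory test for lapses that cannot affect iron exposure, Hb response or Hb measurement. The main cost of these arm-neutral items is precision and the loss of validly randomised subjects. On assumed miss rates of 0.5–1%, exact power moves from 78.7% to about 77% (clustered) or 75–72% (independent), provided the losses come on top of the 20%. The documents do not support saying that the stated power is lost.

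The dosing items create an unequal chance of exclusion (7 against 2 administrations in the protocol's example), with a shift of a few points at most under the assumptions shown and no fixed direction. The documents do not support a claim that the rule favours either product. The unresolved TBD items are a separate gap in pre-specification. Severity: should fix.

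**What to change.** 1. In SAP 3.3, separate Major for reporting from exclusion from the PPS. State that missing vital signs, chemistry (Visits 2 to 6), urinalysis, the Visit 6 pregnancy test and late SAE reporting do not exclude. Keep as exclusions the deviations that can affect iron exposure, Hb response or Hb measurement: wrong treatment; compliance outside 80–120%; on-study prohibited iron, ESA or transfusion; and breaches of Hb-relevant eligibility criteria, including ferritin, TSAT, microcytosis, haemoglobinopathy, B12 or folate deficiency and active infection.
2. Reconcile prohibited medication. SAP 3.3 censors later values and keeps such subjects in the PPS unless they have a major deviation, while Appendix 1 rates the medication itself Major.
3. Decide PPS membership for the TBD dosing items by the existing 80–120% compliance rule, or classify them before database lock without access to treatment arm or post-baseline Hb.
4. Report the FAS result with equal prominence and discuss any disagreement with the PPS. Requiring success in both sets is optional. It would change the decision rule in Protocol 11.7.1 and so need a protocol change.

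Cost: items 1 to 3 are SAP wording and a little programming. The PPS becomes slightly less strict. No new data, visits or subjects are needed.
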